4.2.4 Dosage schedule

- Steroid pulse as short term common treatment for EAA, not used as trial medication: will be received by all subjects:
methylprednisolone 10 mg/kg bw/d (max. 1g) i.v. over 1h for 3 days.
Before starting the steroid pulse, serum levels for potassium have to be checked, if < 3.5 mmol/l substitute oral potassium during d1 through d3 of the pulse. If there are any signs of an acute intervening infection (e.g. fever, other organ involvement, e.g. urinary tract infection or otitis, etc) the steroid pulse must not be administered.
- Oral prednisolone as trial medication:
Anticipated dose:
first month after steroid pulse 0.5 mg/kg bw/d, second month 0.25 mg/kg bw/d, and third month 0.125 mg/kg bw/d in a single morning dose
Individual capsules will be prepared using rounded dose (see 14. Appendix dosage table)

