3.6.1 Inclusion criteria

Subjects meeting all of the following criteria will be considered for admission to the trial:

1. Newly or previously diagnosed but not appropriately treated EAA in children, adolescents and young adults, aged between 6 and 25 years. The diagnosis of EAA must be confirmed by independent review of the findings by an expert panel and must be based on the presence of at least 4 of the following findings:

- * History of appropriate allergen exposure
- * Restrictive lung function (FVC < 80% predicted for age and FVC/FEV1 < 1) testing, if appropriate for age (usually > 5 y)
- * Positive serum precipitins for bird/fungus exposed to (other allergens have rarely, if ever been demonstrated in children)
- * Lymphocytosis in BAL (> 20% of cells are lymphocytes)
- * HRCT showing the characteristic nodular, linear or reticular opacities, and ground glass pattern with increased attenuation.
- * Lung biopsy demonstrating lymphocytic alveolitis, bronchiolitis, and non-caseating histiocytic granulomatas.
- * Controlled allergen exposure followed by characteristic reaction, including fever, coughing, restriction on lung function, hypoxemia/desaturation at rest or with exercise

2. Unchanged inhaled steroids if on; if off, no plans to introduce them in the following 6 months

3. Agreement to home visit by independent study physician

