4.2 Investigational treatments

4.2.1 General information about investigational medicinal product (IMP)

International nonproprietary name (INN): prednisolone
Formulation: hard capsules (capsules with tablets)
Manufacturer: Pharmacy University Medical Center Mainz

Comparative Product (Placebo)

Generic name: Placebo (capsules with placebo tablets)
Formulation: hard capsules
Manufacturer: Pharmacy department University Medical Center Mainz

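### Appendix 14 dosage table: the month-3 prednisolone dose at 13 kg is 1 mg, where the stated 0.125 mg/kg and both neighbouring rows point to 2 mg

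*Protocol*

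**What the plan says.** Protocol section 4.2.4 fixes the trial medication by month: "first month after steroid pulse 0.5 mg/kg bw/d, second month 0.25 mg/kg bw/d, and third month 0.125 mg/kg bw/d in a single morning dose". Each month's rate is half that of the month before. The section then points to the table that turns these rates into milligrams: "Individual capsules will be prepared using rounded dose (see 14. Appendix dosage table". Neither section 4.2.4 nor Appendix 14 states a rounding direction or a rounding step.

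Appendix 14 lists every whole kilogram from 10 to 100, with one daily dose in mg for each of months 1, 2 and 3. The rows at issue, as month 1 / month 2 / month 3, are:

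- 12 kg: 6 / 3 / 2 mg
- 13 kg: 7 / 4 / 1 mg
- 14 kg: 7 / 4 / 2 mg

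Section 4.2.1 describes the product as "Formulation: hard capsules (capsules with tablets" (the tablets are enclosed in the capsule). Section 3.6.1 admits "children, adolescents and young adults, aged between 6 and 25 years" and sets no weight limit.

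**The concern.** The month-3 column reads 2, 1, 2 mg at 12, 13 and 14 kg. A dose proportional to weight cannot fall and then recover as weight rises, whatever single rounding rule is applied. One of the three entries must therefore be wrong, and the middle one stands out.

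This is an operative number, because section 4.2.4 directs that capsules be prepared from the table. A participant in that row on the active arm would receive about 0.077 mg/kg (1/13) in month 3 instead of 0.125 mg/kg. The final reduction would be from 4 to 1 mg, a cut of 75% where the plan intends 50%. What is at stake is agreement between the stated steroid taper and the capsules dispensed. No statistical result depends on it.

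**Working it through.** **Inputs.** Rates of 0.5, 0.25 and 0.125 mg/kg/day for months 1, 2 and 3 (section 4.2.4); 91 weights × 3 months = 273 cells (Appendix 14).

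**Step 1: which rule does the table follow?** Exact dose = weight × rate. Rounding up to the next whole mg reproduces 261 of 273 cells: 83 of 91 in month 1, 91 of 91 in month 2 and 87 of 91 in month 3. Rounding up is thus the table's evident habit, though not a stated rule.

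**Step 2: the four month-3 cells that are not rounded up.**

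| Weight | Exact (weight × 0.125) | Table | Table − exact | Nearest whole mg |
|---|---|---|---|---|
| 10 kg | 1.250 | 1 | −0.250 | 1 |
| 11 kg | 1.375 | 1 | −0.375 | 1 |
| 13 kg | 1.625 | 1 | −0.625 | 2 |
| 17 kg | 2.125 | 2 | −0.125 | 2 |

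The entries at 10, 11 and 17 kg are the nearest whole mg and are defensible. The 13 kg entry is neither rounded up nor nearest. Its relative error is (1 − 1.625)/1.625 = −38.5%. The only whole-mg rule that yields 1 mg at 13 kg is rounding down. Rounding down would also give 1 mg at 12 kg (exact 1.5) and at 14 kg (exact 1.75), where the table has 2 mg.

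**Step 3: is it unique?** The other 12 − 4 = 8 cells that are not rounded up are all in month 1 and lie above the exact dose. No cell outside the four in step 2 is therefore below its exact dose, and 13 kg is the only one more than 0.5 mg below. It is also the only fall in any column: month 3 drops from 2 to 1 mg between 12 and 13 kg.

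**Step 4: the taper.** The stated month-3 to month-2 ratio is 0.125/0.25 = 0.5. At 13 kg the table gives 1/4 = 0.25, the lowest of the 91 rows. The next lowest is 1/3 = 0.33, at 10 and 11 kg. With 2 mg the ratio would be 2/4 = 0.5, as section 4.2.4 intends.

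**Step 5: total exposure at 13 kg, over three 28-day months.** Stated: 28 × 13 × (0.5 + 0.25 + 0.125) = 28 × 13 × 0.875 = 318.5 mg. Table: 28 × (7 + 4 + 1) = 336 mg, which is 336/318.5 − 1 = +5.5%. The row is not under-dosed in total, because months 1 and 2 are rounded up (6.5 to 7 mg and 3.25 to 4 mg). The discrepancy lies in the month-3 daily dose and the taper.

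**Step 6: the eight month-1 cells.**

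| Weight | Exact (weight × 0.5) | Table | Difference |
|---|---|---|---|
| 77 kg | 38.5 | 40 | +3.9% |
| 78 kg | 39.0 | 40 | +2.6% |
| 87 kg | 43.5 | 45 | +3.4% |
| 88 kg | 44.0 | 45 | +2.3% |
| 95 kg | 47.5 | 50 | +5.3% |
| 96 kg | 48.0 | 50 | +4.2% |
| 97 kg | 48.5 | 50 | +3.1% |
| 98 kg | 49.0 | 50 | +2.0% |

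They sit in unbroken bands with the rows above them (77–80 kg at 40 mg, 87–90 kg at 45 mg, 95–100 kg at 50 mg), and the column never falls.

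**The case against.** **The row may never be used.** Inclusion starts at age 6, a child of that age is unlikely to weigh 13 kg, and about half of the 45 planned participants receive prednisolone. This stands as to consequence. It does not make the entry right: the row is in the current table and no weight criterion excludes it.

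**Section 4.2.4 calls the doses anticipated and rounded, with no rule given, so some deviation is allowed.** Also true, and it is why 10, 11 and 17 kg are left alone. It cannot cover a dose that drops at 13 kg and returns at 14 kg.

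**The 1 mg might offset the upward rounding of months 1 and 2.** The three doses add to 6 + 3 + 2 = 11, 7 + 4 + 1 = 12 and 7 + 4 + 2 = 13 mg at 12, 13 and 14 kg, a smooth run. But the protocol sets no cumulative target. It sets a daily dose for each month, and that is what the cell misses.

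**A reader might go further and call the eight month-1 cells errors as well.** They match neither rounding up nor nearest-mg rounding, and nearby rows use values such as 38, 43 and 47 mg. The documents do not support that reading. No rounding step is stated, 40, 45 and 50 mg are themselves rounded doses, and the excess is 2.0% to 5.3%. The product consists of tablets in capsules, so a tablet-strength reason is possible, though none is given.

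**A reader might also infer that a 13 kg child is under-dosed overall, or that the efficacy comparison is compromised.** Neither follows: total exposure in that row is 5.5% above the stated dose, and the 6-month FVC comparison is not materially touched.

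**Conclusion.** The point holds for one cell. Month 3 at 13 kg should not be 1 mg: it is 0.625 mg (38%) below the stated daily dose, it breaks the order of the column, and it turns a halving into a 75% cut. This rests only on the rates in section 4.2.4 and the entries in Appendix 14.

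Severity is minor. That judgement rests on the assumption that participants aged 6 or over will rarely if ever weigh 13 kg; the protocol gives no weight data to confirm it. If such a child were enrolled on the active arm, the effect would be a month-3 daily dose that is too low and too steep a last step. The month-1 values are at most a matter to confirm.

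**What to change.** Set month 3 at 13 kg in Appendix 14 to 2 mg, and check that the pharmacy's own preparation list carries the same value. Two mg is the nearest whole mg (0.375 mg above the exact dose, against 0.625 mg below for 1 mg), matches 12 and 14 kg, and restores the halving from month 2. It raises the row total to 28 × (7 + 4 + 2) = 364 mg, the same as the 14 kg row and 364/318.5 − 1 = 14.3% above the stated dose. That follows from rounding up in all three months.

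Leave month 3 at 10, 11 and 17 kg unchanged. Optionally, ask the pharmacy to confirm that 40, 45 and 50 mg in month 1 are intended; no change is required there.

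The cost is one corrected table cell, which is negligible.

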4.2.5 Overdose instructions

The effects of accidental ingestion of large quantities of prednisolone over a very short period of time have not been reported.

4.2.6 Treatment assignment

The trial medication will be administered only to subjects included in this trial.

Subjects withdrawn from the trial retain their identification codes (e.g. randomization number). New subjects will always receive a new identification code.

4.2.7 Treatment after the end of the trial

Treatment after the end of the trial is at the discretion of the investigator.

4.2.8 Packaging and labelling

The trial medication will be labelled according to local regulations.

The trial medication will be packed by pharmacy university medical centre Mainz.

Statements will be printed on the label(s) as required by local regulations.

4.2.9 Drug storage, supplies and accountability

The investigator will take inventory and acknowledge the receipt of all shipments of the trial medication. All trial medication must be kept in a locked area with access restricted to designated trial staff.

The trial medication must be dryly stored in accordance with manufacturer's instructions.

The investigator will also keep accurate records of the quantities of trial medication dispensed, used, and returned by each subject on the drug accountability form.

The site monitor will periodically check the supplies of trial medication held by the investigator to verify the correct accountability of all trial medication used. At the end of the trial, all unused trial medication and all medication containers will be completely returned to pharmacy Mainz in case no other procedure is agreed.

It will be assured that a final drug accountability report is prepared and maintained by the investigator.

4.2.10 Procedures for monitoring subject compliance

Trial medication will be dispensed to the subjects by the investigator.

Subjects will be instructed to bring all trial medication to the trial site at every visit (including all empty packages and unused trial medication), compliance will be assessed. Details will be recorded in the CRF and on the drug accountability form in the investigator site file.

4.2.11 Medication intake

Medication intake should take place with the meals or shortly after the meals. Whole capsules will be taken with liquid (50-100ml water, tea or apple juice).

4.3 Not permitted medication

The following concomitant treatments are not permitted during the trial:

Other systemic glucocorticosteroids as concomitant treatments are not permitted during the trial. However their usage as rescue therapy by the attending physician is possible and must be documented appropriately. Inhaled steroids are left unchanged if patient is currently on; if off, do not introduce them in the following 6 months.

For interactions with other medication and warnings please see 4.2.3.

4.4 Open rescue treatment if lung function does not improve

With removal of the allergen by hospitalization and cleaning of the home from offending allergens which is usually done during the initial hospital stay, and after application of the 3d steroid boost to all subjects, a steady improvement in lung function is anticipated. This will be closely monitored by monthly lung function measurements in the first 3 months and at 6 months or additional visits at the discretion of the treating physician. FVC (% predicted) is expected to increase from visit to visit.

If this is not the case, continuing allergen exposure must be considered and a re-evaluation of the allergen elimination has to be performed.

If there is no appropriate improvement of lung function despite appropriate allergen elimination, an open rescue treatment with oral prednisolone (0.5 mg/kg bw/d) should be given till the patient's lung function improves. An alternative may be pulsed methylprednisolone (10 mg/kg bw/d). Extra visits at the discretion of the treating physician may be scheduled.

If the result of the oral prednisolone is not satisfying, re-evaluation of the diagnosis and possibly de-blinding of the study medication should be considered. Alternative medication, including steroid sparing drugs may be considered.

All rescue treatments necessary will be recorded and the cumulative amount of steroids necessary used as a secondary outcome variable.

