In this study we propose to use a single three day boost of steroids in order to allow a rapid symptomatic recovery (as described below) of the children and then randomize to a relatively low dose taper of prednisolone, as frequently done in current practice.

To our knowledge there are no randomized trials, even in adults (in patients) with EAA due to bird allergens.

One study of 93 patients with farmer's lung compared patients treated with glucocorticoids for 4 or 12 weeks to control patients treated with antigen avoidance alone (Mönkäre 1983). Symptom resolution was more rapid among the glucocorticoid-treated groups, but no differences in the course of disease among the three

groups were noted after six months. The 12 week glucocorticoid regimen offered no advantage over the four week regimen. This study is limited by the fact that the non-glucocorticoid-treated group was less severe and that the study was not blinded.

A trial of 36 persons with acute farmer's lung randomized patients to eight weeks of treatment with either prednisolone or placebo (Kokkarinen 1992). After one month, there was a significant improvement in DLCO in the prednisolone-treated group, but no statistically significant differences in FVC, FEV1, or DLCO were found after that time until follow-up was terminated at five years.

There are yet no randomized controlled trials in pediatric EAA patients at all.

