3.4 Secondary endpoints

Each patient will be classified as a responder or non-responder. A patient is considered as a responder, if the FVC value after 6 months is more than or equal to 93% of the norm values tabulated by Quanjer PH., et al. 2013.

Further secondary endpoints are:

Relative change from baseline through month 6 compared to change from placebo for

- * desaturation with standardized exercise test for children
- * Borg scale
- * Quality-of-life
- * Health economics
- * Weight for height
- * Open usage of rescue glucocorticosteroids (mg/kg/6 months)

Relative change from baseline through month 3 compared to change from placebo for

- * forced vital capacity (FVC)
- * desaturation with standardized exercise test for children
- * Borg scale
- * Quality-of-life
- * Health economics
- * Weight for height
- * Open usage of rescue glucocorticosteroids (mg/kg/6 months)

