6.3 Other assessments

6.3.1 *Prior and concomitant illnesses*

Relevant additional illnesses present at the time of informed consent are regarded as concomitant illnesses and will be documented on the appropriate pages of the case report form (CRF).

6.3.2 *Prior and concomitant treatments*

Relevant additional treatments administered to the subjects on entry to the trial or at any time during the trial are regarded as concomitant treatments and must be documented on the appropriate pages of the CRF.

For example in case of insufficient improvement of the symptoms, glucocorticoids may be administered to the subject and again searched for other sources of the allergen.

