7.3 Efficacy analyses

Efficacy:

The analyses will be specified more detailed in the statistical analysis plan (SAP). Descriptive statistics of qualitative data will consist of absolute and relative frequencies. For quantitative data the number of observations, mean, standard deviation, minimum and maximum will be presented.

The primary population for the analyses of efficacy is the randomized Population without major protocol violations.

7.3.1 *Definition and analysis of primary endpoint*

The primary analysis variable is the improvement in FVC (difference after 6 months and baseline). The 6 months and baseline FVC values will be given in percent deviation from the norm values tabulated by Quanjer PH., et al. 2013.

A difference between the changes in placebo and active treatment is considered not significant if FVC differences are < 7%. The working hypothesis of the study is that the placebo is not inferior to the prednisolone intervention.

The improvement in FVC will be compared between groups within an analysis of covariance (ANCOVA). Treatment will serve as a fixed factor and the baseline FVC value as a covariate. The primary analysis population will consist of all randomized patients without any major protocol violations. The two-sided 90% confidence interval for the treatment difference will be calculated. Sensitivity analyses will be performed by analyzing the same analysis model for all randomized patients. Additionally, the primary parameter will be analyzed by ANCOVA with additional terms for sex and height. Center effects will be explored by descriptive statistics. Missing values will not be replaced.

If appropriate, a Bayesian analysis with a suited prior distribution will be considered. This will be specified in the statistical analysis plan (SAP).

7.3.2 *Analysis of secondary endpoints*

All analysis of secondary endpoint will be interpreted purely exploratory. Descriptive statistics will be displayed for all

- Response according to the primary analysis variable: Each patient will be classified as a responder or non-responder. A patient is considered as a responder, if the FVC value after 6 months is more than or equal to 93% of the norm values tabulated by Quanjer PH., et al. 2013 and if the patient did not take any glucocorticoid rescue medication. Responders will be analysed by a Chi-Square Test.

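### Sections 4.4 and 6.3.2 set different conditions for open steroid rescue, so the rescue-dose endpoint and, under section 7.3.2, responder status can depend on which section a site follows

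*Protocol*

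**What the plan says.** Three places in the protocol deal with open glucocorticoid rescue.

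- **Section 4.4**, the dedicated rescue section, expects FVC to rise from visit to visit. If it does not, "continuing allergen exposure must be considered and a re-evaluation of the allergen elimination has to be performed". Then: "If there is no appropriate improvement of lung function despite appropriate allergen elimination, an open rescue treatment with oral prednisolone" should be given until lung function improves.
- **Section 6.3.2**, on documenting concomitant treatment, gives an example: "in case of insufficient improvement of the symptoms, glucocorticoids may be administered to the subject and again searched for other sources of the allergen".
- **Section 4.3** prohibits other systemic glucocorticosteroids and then makes an exception: "However their usage as rescue therapy by the attending physician is possible and must be documented appropriately". It names no condition and does not refer to 4.4.

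Two endpoints use rescue. Section 4.4 states: "All rescue treatments necessary will be recorded and the cumulative amount of steroids necessary used as a secondary outcome variable". Section 3.4 lists this dose among the secondary endpoints at months 3 and 6. For responder status, section 7.3.2 requires FVC of at least 93% of norm "and if the patient did not take any glucocorticoid rescue medication". Section 3.4 and the synopsis carry only the FVC part: "A patient is considered as a responder, if the FVC value after 6 months is more than or equal to 93" percent of norm. Section 7.3.2 treats all secondary analyses as purely exploratory.

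**The concern.** A physician who gives steroids because symptoms are slow to improve, and repeats the allergen search at the same time, acts within the example in 6.3.2 and the exception in 4.3. The same course is not the one 4.4 describes, which starts from lung function and puts the allergen re-evaluation first. Two sites with the same patient could record different rescue doses, and under 7.3.2 a different responder status, while each follows the protocol.

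These are instructions to sites. A statistical analysis plan can say how rescue is analysed, but it cannot make the decision to give rescue uniform afterwards. Local habit will not do so either: 45 patients over about 40 sites is roughly one patient per site.

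The order also bears on the trial's rationale. Sections 1.1 and 1.2 argue that steroids can disguise continuing allergen exposure, and the re-evaluation step in 4.4 guards against that. The example in 6.3.2 does not make it a condition.

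**Working it through.** **Step 1: the rules side by side.**

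| | 4.4 | 6.3.2 | 4.3 |
|---|---|---|---|
| Trigger | Lung function not improving appropriately | Symptoms not improving sufficiently (an example) | None stated |
| Allergen re-check | Required, and elimination must be appropriate | Named together with steroids, not a precondition | Not mentioned |
| Strength | *Should* be given | *May* be administered | Possible, at the attending physician's choice |

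Two sections state a condition, and they differ on trigger, precondition and strength. The third is silent.

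**Step 2: which endpoints depend on it.** Rescue dose depends on the rule directly. Responder status depends on it directly only under 7.3.2. Under 3.4 and the synopsis the direct effect is zero, because rescue is not part of the definition.

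**Step 3: size for the responder rate under 7.3.2.** The protocol gives no expected rescue rate and no expected responder rate, so there is no figure of its own to reproduce.

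- Inputs: 40 evaluable patients (sections 3.2 and 7.1) and 1:1 allocation (section 3.5.1), so 40 / 2 = 20 per arm.
- One patient is 1 / 20 = 5 points. This applies only to a rescued patient who would otherwise have reached 93% of norm. A rescued patient below 93% is a non-responder either way and moves the rate by 0.
- Assume one reading of the rule rescues an extra 10% to 25% of one arm, which is 2 to 5 of 20 patients. The ceiling is a fall of 10 to 25 points, reached only if all of them would have been at or above 93%.
- Assume instead that 60% reach 93%, independently of rescue. The fall is then 0.60 × 10 = 6 to 0.60 × 25 = 15 points.

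**Step 4: the same arithmetic between arms.** Assume 60% of each arm reach 93%, rescue independent of FVC, and 10% rescued on prednisolone, so the prednisolone responder rate is 0.60 × 0.90 = 54%.

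| Placebo rescued | Placebo responders under 7.3.2 | Placebo minus prednisolone, 7.3.2 | Direct difference, 3.4 |
|---|---|---|---|
| 10% | 0.60 × 0.90 = 54% | 0 | 0 |
| 20% | 0.60 × 0.80 = 48% | −6 points | 0 |
| 30% | 0.60 × 0.70 = 42% | −12 points | 0 |
| 40% | 0.60 × 0.60 = 36% | −18 points | 0 |

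The rescue shares and the 60% are assumptions chosen to show scale. The protocol supplies none of them.

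**The case against.** The strongest reply is that 4.4 is the rescue section and the other two passages do not compete with it. Section 4.3 is an exception clause placed shortly before 4.4, and its silence contradicts nothing. Section 6.3.2 concerns what to document, its sentence is an example, and it is permissive, so a site that follows 4.4 breaks nothing in 6.3.2. Much of this stands. It would be wrong to say that three sections give three triggers. It would also be wrong to say that 6.3.2 reverses the order: it joins the two actions with *and*, which is not a steroids-first rule. What remains is that 6.3.2 describes steroid use on a condition 4.4 does not contain and without the step 4.4 requires.

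A second reply is that 4.4 itself sets no threshold for appropriate improvement, so matching the wording would not fully standardise rescue. That is true, but it does not justify two different kinds of trigger.

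A third reply is that allergen control does not hang on rescue alone. Section 4.1 has a home check around day 56, and Table 1 has a call at day 126 about symptoms and elimination status. This weakens the masking argument but does not settle which rule governs rescue.

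A reader might infer that the symptom trigger falls mainly on placebo. Section 1.3 does report "Symptom resolution was more rapid among the glucocorticoid-treated groups", but in a farmer's lung study that the protocol itself describes as unblinded and with a less severe untreated group. Here every patient first receives a steroid pulse and treatment is blinded. A lung-function trigger could lean the same way, since section 1.1 describes steroids as improving symptoms and lung function together. Blinding would not remove an imbalance driven by real symptom differences, so the direction is plausible, but no passage establishes it.

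**Conclusion.** The point holds as an inconsistency between 4.4 and 6.3.2, left open by 4.3. It affects two secondary, exploratory endpoints: rescue dose directly, and responder status under 7.3.2 only. The firm figure is 5 points of an arm's responder rate for each rescued patient who would otherwise have reached 93% of norm, assuming 20 evaluable per arm. The larger ranges in the working rest on assumed rescue and response rates.

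A reader might go further and conclude that the discrepancy biases the primary month-6 FVC comparison towards non-inferiority. The documents do not support that as a consequence of this conflict. Open prednisolone can reach the placebo arm under 4.4 alone, the arm balance of rescue is unknown, and the handling of FVC after rescue may be set out in an analysis plan that is not available here.

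That 7.3.2 and 3.4 define a responder differently is a separate contradiction. It matters here because it decides whether the responder consequence exists at all.

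**What to change.** Reconcile sections 4.4 and 6.3.2 so that both carry one trigger and one order relative to the allergen re-check, and have 4.3 refer to that rule. Which trigger and which order is a clinical decision for the sponsor; this point does not favour either.

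If the eCRF does not already do so, record for each rescue course the trigger met (FVC, symptoms or other), the FVC at the start of the course, and whether allergen elimination had been re-checked first. Rescue dose and responder status can then be described by trigger even if practice varies.

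The cost is minor amendment wording and about three eCRF fields. No visit, measurement or sample size changes.
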